5.4.3. Vital Signs

Several analyses of vital signs data will be presented. Descriptive statistics of the highest and lowest values at each visit and the highest and lowest value at any post-baseline visit(including unscheduled post-baseline measurements) will be summarized by treatment group for each vital sign parameter (heart rate, blood pressure, respiratory rate, and temperature). The change from baseline to the highest and lowest values at each post-baseline visit and the highest and lowest value at any post-baseline visit (including unscheduled post-baseline measurements) will be provided for each vital sign parameter by treatment group. Change from baseline to the highest and lowest values at each post-baseline visit will be calculated for each subject and parameter as the highest or lowest value at the specified visit minus the baseline value. For this summary, data for subjects who are no longer hospitalized at a particular visit will be included in both summaries of highest and lowest value for that visit, since highest and lowest values are only captured in the eCRF for visits during which a subject is hospitalized.

A summary of potentially clinically significant (PCS) values, identified as values meeting both the criterion value and the change from baseline criterion listed in Table 5-1, will be provided for the worst post-baseline value (which includes unscheduled post-baseline measurements). Both the highest and lowest daily vital signs values will be entered into the eCRF for hospitalized subjects. The highest daily value will be used to assess PCS High (CH) values; the lowest daily value will be used to assess PCS Low (CL). The incidence of PCS values will be summarized by treatment group for the worst post-baseline value and will be listed and flagged in by-subject listings.

For all analyses of temperature, temperatures obtained by non-oral methods of rectal or tympanic will be converted to oral temperatures by subtracting 0.3°C from the temperature in °C. Temperatures obtained by temporal methods will be converted to oral temperatures by adding 0.3°C to the temperature in °C.

A by subject listing of vital signs reported at each visit will be provided.

CONFIDENTIAL Page 45 of 56

Table 5-1: Criteria for Potentially Clinically Significant Vital Signs

Vital Sign Parameter	Flag	Criterion Value	Change from Baseline
Contalia Dia ad Duaganna (nome IIa)	High (CH)	≥180 mm Hg	Increase of ≥20 mmHg
Systolic Blood Pressure (mm Hg)	Low (CL)	≤90 mm Hg	Decrease of ≥20 mmHg
Disatelia Disad Dassaura (m.m. Ha)	High (CH)	≥105 mm Hg	Increase of ≥15 mmHg
Diastolic Blood Pressure (mm Hg)	Low (CL)	≤50 mm Hg	Decrease of ≥15 mmHg
Heart Date (bear)	High (CH)	≥120 bpm	Increase of ≥15 bpm
Heart Rate (bpm)	Low (CL)	≤50 bpm	Decrease of ≥15 bpm
Tamanatura (OC)	High (CH)	>38°C	Increase of ≥1°C
Temperature (°C)	Low (CL)	≤36 °C	Decrease of ≥1°C
Descriptions Date (breaths/minute)	High (CH)	≥30 breaths/minute	Increase of ≥10 breaths/minute
Respiratory Rate (breaths/minute)	Low (CL)	≤8 breaths/minute	Decrease of ≥4 breaths/minute

5.4.4. Electrocardiogram

Descriptive statistics for heart rate, PR interval, RR interval, QRS interval, QT interval, and QT interval with Fridericia correction (QTcF) at Baseline and the EOT visit and the change from baseline at the EOT visit will be summarized by treatment group for subjects in the Safety population. Change from baseline will be calculated for each subject as the value at the EOT visit minus the baseline value. QTcF will be derived programmatically using the QT and RR intervals captured in the eCRF according to the following formula (Fridericia):

$$QT_cF = \frac{QT}{\sqrt[3]{RR}}$$

The number and percentage of subjects with any post-baseline increase in QTcF and any post-baseline increase of >30 msec or >60 msec in QTcF will be summarized by treatment group. The number and percentage of subjects with a post-baseline QTcF of >450 msec or >500 msec will also be summarized by treatment group. The number and percentage of subjects with a post-baseline increase in QTcF of >30 msec resulting in a post-baseline QTcF of >450 msec or >500 msec will also be summarized by treatment group. The distribution of QTcF values (\leq 450 msec, >450 - \leq 480 msec, >480 - \leq 500 msec, and >500 msec) at EOT and the distribution of change from baseline in QTcF values at EOT (0 or less (no increase), 1-29 msec, 30-60 msec, and >60 msec) will be summarized by treatment group for subjects in the Safety population.

A by subject listing of all measurements obtained from ECG assessments will be provided.

5.4.5. Physical and Retinal Examinations

Physical exam findings from Screening, Day 14 (± 1), Day 28 (± 2), and the FU visit will be presented in a by-subject listing. Abnormal findings from retinal examinations and whether or not the subject had evidence of *Candida* endophthalmitis will be provided in a by-subject listing.

CONFIDENTIAL Page 46 of 56

5.4.6. Radiological Evaluations

Results of radiological testing will be provided in by-subject listings.

CONFIDENTIAL Page 47 of 56

6. APPENDICES

6.1. Appendix 1: Directionality of Worst Laboratory Parameters

Table 6-1: Directionality of Worst Laboratory Parameters

Laboratory Test	Parameter	Worst Value
Hematology	Hemoglobin	Lowest value
	Hematocrit	Lowest value
	White blood cell count	Both highest value and lowest value
	Neutrophils	Both highest value and lowest value
	Lymphocytes	Both highest value and lowest value
	Monocytes	Both highest value and lowest value
	Eosinophils	Highest value
	Basophils	Highest value
	Red blood cell count	Lowest value
	Platelets	Both highest value and lowest value
Chemistry	Blood urea nitrogen (BUN)	Highest value
	Bilirubin (total and direct)	Highest value
	Alkaline phosphatase (ALP)	Highest value
	Aspartate aminotransferase (AST/SGOT)	Highest value
	Alanine aminotransferase (ALT/SGPT)	Highest value
	Albumin	Lowest value
	Sodium	Both highest value and lowest value
	Potassium	Both highest value and lowest value
	Chloride	Both highest value and lowest value
	Glucose	Both highest value and lowest value
	Creatinine	Highest value
	Total protein	Both highest value and lowest value
	Calcium	Both highest value and lowest value
	Bicarbonate	Both highest value and lowest value
Coagulation	Prothrombin time	Highest value
	International normalized ratio (INR)	Highest value
	Partial thromboplastin time (PTT)	Highest value
	Activated PTT	Highest value

CONFIDENTIAL Page 48 of 56

6.2. Appendix 2: Clinical Laboratory Toxicity Grading Scales

Table 6-2: Hematology and Coagulation Toxicity Grading Scale

Hematology and Coagulation							
Parameter	Direction	Grade 0 / Normal	Grade 1	Grade 2	Grade 3	Grade 4	Source
Hemoglobin	Decrease	>10.5 gm/dL	9.5 – 10.5 gm/dL	$8.0-9.4 \\ \text{gm/dL}$	6.5 – 7.9 gm/dL	<6.5 gm/dL	DMID
WBCs	Increase	1,000- 10,999 /mm ³	11,000- 13,000 /mm ³	13,000- 15,000 /mm ³	15,000- 30,000 /mm ³	>30,000 or <1,000 /mm ³	DMID
Absolute Neutrophil Count	Decrease	>1500 /mm ³	1000-1500 /mm ³	750-999 /mm ³	500-749 /mm ³	<500 /mm ³	DMID
Platelets	Decrease	>99,999 /mm ³	75,000- 99,999 /mm ³	50,000- 74,999 /mm ³	20,000- 49,999 /mm ³	<20,000 /mm ³	DMID
Prothrombin Time (PT)	Increase	<1.01 ×ULN	1.01-1.25 ×ULN	1.26-1.5 ×ULN	1.51-3.0 ×ULN	>3 ×ULN	DMID
Activated Partial Thromboplastin (APPT)	Increase	<1.01 ×ULN	1.01-1.66 ×ULN	1.67-2.33 ×ULN	2.34-3 ×ULN	>3 ×ULN	DMID

CONFIDENTIAL Page 49 of 56

Table 6-3: Chemistry Toxicity Grading Scale

Chemistry							
Parameter	Direction	Grade 0 / Normal	Grade 1	Grade 2	Grade 3	Grade 4	Source
Blood urea nitrogen (BUN)	Elevation	<1.25 ×ULN	1.25-2.5 ×ULN	2.6-5 ×ULN	5.1-10 ×ULN	>10 ×ULN	DMID
Bilirubin (total and	Hyperbilirubinemia (when accompanied by any increase in other liver function test)	<1.1 ×ULN	1.1-<1.25 ×ULN	1.25-<1.5 ×ULN	1.5-1.75 ×ULN	>1.75 ×ULN	DMID
direct)	Hyperbilirubinemia (when other liver functions are in the normal range)	<1.1 ×ULN	1.1-<1.5 ×ULN	1.5-<2.0 ×ULN	2.0-3.0 ×ULN	>3.0 ×ULN	DMID
Albumin	Hypoalbuminemia		3.0 g/dL- <lln< td="">2.0-<3 g/dL	<2.0 g/dL	N/A	CTCAE	</lln<>	2.0-<3 g/dL	<2.0 g/dL	N/A	CTCAE
Co diam.	Hyponatremia	>135- <146 mEq/L	130-135 mEq/L	123-129 mEq/L	116-122 mEq/L	<116 mEq/L	DMID
Sodium	Hypernatremia	>135- <146 mEq/L	146-150 mEq/L	151-157 mEq/L	158-165 mEq/L	>165 mEq/L	DMID
Datassiana	Hypokalemia	>3.4-<5.6 mEq/L	3.0-3.4 mEq/L	2.5-2.9 mEq/L	2.0-2.4 mEq/L	<2.0 mEq/L	DMID
Potassium	Hyperkalemia	>3.4-<5.6 mEq/L	5.6-6.0 mEq/L	6.1-6.5 mEq/L	6.6-7.0 mEq/L	>7.0 mEq/L	DMID
	Hypoglycemia	>64-<116 mg/dL	55-64 mg/dL	40-54 mg/dL	30-39 mg/dL	<30 mg/dL	DMID
Glucose	Hyperglycemia (nonfasting and no prior diabetes)	>64-<116 mg/dL	116-160 mg/dL	161-250 mg/dL	251-500 mg/dL	>500 mg/dL	DMID
Creatinine	Elevation	<1.1 ×ULN	1.1-1.5 ×ULN	1.6-3.0 ×ULN	3.1-6 ×ULN	>6 ×ULN	DMID
Total protein							
Calcium	Hypocalcemia	>8.4- <10.6 mg/dL	8.4-7.8 mg/dL	7.7-7.0 mg/dL	6.9-6.1 mg/dL	<6.1 mg/dL	DMID
	Hypercalcemia	>8.4- <10.6 mg/dL	10.6-11.5 mg/dL	11.6-12.5 mg/dL	12.6-13.5 mg/dL	>13.5 mg/dL	DMID
Bicarbonate	Low		16 mEq- <lln< td="">11.0-15.9 mEq/L	8.0-10.9 mEq/L	<8.0 mEq/L	DAIDS	</lln<>	11.0-15.9 mEq/L	8.0-10.9 mEq/L	<8.0 mEq/L	DAIDS

CONFIDENTIAL Page 50 of 56

Table 6-4: Enzymes Toxicity Grading Scale

Enzymes							
Parameter	Direction	Grade 0 / Normal	Grade 1	Grade 2	Grade 3	Grade 4	Source
Alkaline phosphatase (ALP)	Elevation	<1.1 ×ULN	1.1-<2.0 ×ULN	2.0-<3.0 ×ULN	3.0-8.0 ×ULN	>8 ×ULN	DMID
Aspartate aminotransferase (AST/SGOT)	Elevation	<1.1 ×ULN	1.1-<2.0 ×ULN	2.0- <3.0 ×ULN	3.0- 8.0 ×ULN	>8 ×ULN	DMID
Alanine aminotransferase (ALT/SGPT)	Elevation	<1.1 ×ULN	1.1-<2.0 ×ULN	2.0-<3.0 ×ULN	3.0-8.0 ×ULN	>8 ×ULN	DMID

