5.4.2. Clinical Laboratory Data

Several analyses of clinical laboratory data will be presented. For descriptive statistics of actual values and the change from baseline, values will be normalized against normal ranges from a common source (US National Library of Medicine [NLM], MedlinePlus) according to the following Scale Model formula (Karvanen):

$$s = x \frac{U_S}{U_X}$$

where s = the individual laboratory value normalized against the laboratory normal range from the common source; x = the original individual laboratory value; U_x is the upper limit of the normal range for an individual laboratory parameter; U_s is the upper limit of the laboratory normal range for that laboratory parameter from the common source.

Descriptive statistics (based on Systeme Internationale [SI] units) for chemistry, hematology and coagulation (baseline and unscheduled post-baseline only), and urinalysis (only pH and specific gravity) parameters as well as the change from baseline, will be summarized by treatment group for all study visits and for the worst overall post-baseline value. The directionality for determining the worst overall post-baseline value is provided in SAP Section 6.1. Change from baseline will be calculated for each subject at the specified time point as the value at the specified time point minus the baseline value.

The normalized laboratory values will be classified by toxicity grade according to the toxicity grading scales in SAP Section 6.2, which are based on the Division of Microbiology and Infectious Diseases (DMID) Adult Toxicity Scale, November 2007, the Division of AIDS (DAIDS) Table for Grading the Severity of Adult and Pediatric Adverse Events, December 2004, and the National Cancer Institute Common Terminology Criteria for Adverse Events (CTCAE, Version 4.0), Publish Date: 28 May 2009.

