Shift tables will be presented to show the number of subjects with each toxicity grade at baseline versus each post-baseline visit and the worst post-baseline grade (including any unscheduled visits). For those laboratory parameters for which high toxicity grades are specified for both low and high values (eg, sodium, potassium), shifts in toxicity will be presented for high and low toxicities separately. The percentages will be based on the number of subjects with both a baseline and post-baseline (at the specified visit) assessment of the specific laboratory parameter. The number and percentage of subjects with at least a 2-grade increase from baseline at any post-baseline study visit, including unscheduled visits, will be summarized by laboratory

CONFIDENTIAL Page 44 of 56

parameter and treatment group. Percentages for each lab test will be based on the number of subjects with both a baseline and a post-baseline evaluation of the particular laboratory test. A listing will be provided which provides all results for a given laboratory test for subjects who have at least one 2-grade increase from baseline.

The number and percentage of subjects in each treatment group with an elevated transaminase level (>3 ×ULN, >5 ×ULN, and >10 ×ULN), an elevated total and direct bilirubin level (>1.5 ×ULN and >2 ×ULN) will be presented by study visit. A listing of subjects who meet the laboratory criteria for Hy's law will also be provided for Parts A and B combined. Two alternative definitions of criteria for Hy's law will be considered, defined as 1) (ALT or AST) >3 ×ULN, ALP \leq 2.0 ×ULN, and total bilirubin >1.5 ×ULN; and 2) (ALT or AST) >3 ×ULN, ALP \leq 2.0 ×ULN, and total bilirubin >2 ×ULN. Using a conservative approach for detecting any potential Hy's law cases, subjects meeting either criteria based on any combination of post-baseline laboratory results, irrespective of their temporal association, will be listed. All laboratory results for the parameters included in the criteria will be presented by visit for all subjects who meet the criteria.

Detailed patient listings of all laboratory data collected during the study will be provided. Laboratory values outside normal limits will be identified in the patient data listings. A column will display any applicable toxicity grading of the laboratory value.

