6.3. Appendix 3: Laboratory Normals

Table 6-5: Hematology Laboratory Normals

Hematology						
	LLN	ULN	Source			
Hemoglobin						
Male	13.8 gm/dL	17.2 gm/dL	NLM			
Female	12.1 gm/dL	15.1 gm/dL	NLM			
Hematocrit						
Male	40.7%	50.3%	NLM			
Female	36.1%	44.3%	NLM			
White blood cell count	4,500 cells/mcL	10,000 cells/mcL	NLM			
Differential leukocyte count						
Neturophils	40%	60%	NLM			
Lymphocytes	20%	40%	NLM			
Monocytes	2%	8%	NLM			
Eosinophils	1%	4%	NLM			
Basophils	0.50%	1%	NLM			
Red blood cell count						
Male	4.7 ×10 ⁶ cells/mcL	6.1 ×10 ⁶ cells/mcL	NLM			
Female	4.2 ×10 ⁶ cells/mcL	5.4 ×10 ⁶ cells/mcL	NLM			
Platelet count	150,000/dL	450,000/dL	NLM			

CONFIDENTIAL Page 51 of 56

Table 6-6: Coagulation Laboratory Normals

Coagulation						
	LLN	ULN	Source			
Prothrombin time (International Normalized Ratio)						
No warfarin	11 seconds (0.8)	13.5 seconds (1.1)	NLM			
With warfarin	(2.0)	(3.0)	NLM			
Partial thromboplastin time (PTT) or activated partial thromboplastin time (APTT)						
No warfarin	25 seconds	35 seconds	NLM			

Table 6-7: Serum Chemistry Laboratory Normals

Serum Chemistry						
	LLN	ULN	Source			
Blood urea nitrogen	6 mg/dL	20 mg/dL	NLM			
Bilirubin						
Direct	0 mg/dL	0.3 mg/dL	NLM			
Total	0.3 mg/dL	1.9 mg/dL	NLM			
Alkaline phosphatase (ALP)	44 IU/L	147 IU/L	NLM			
Aspartate aminotransferase (AST/SGOT)	10 U/L	34 U/L	NLM			
Alanine aminotransferase (ALT/SGPT)						
Male	10 U/L	40 U/L	NLM			
Female	7 U/L	35 U/L	NLM			
Albumin	3.4 g/dL	5.4 g/dL	NLM			
Sodium	135 mEq/L	145 mEq/L	NLM			
Potassium	3.7 mEq/L	5.2 mEq/L	NLM			
Chloride	96 mEq/L	106 mEq/L	NLM			
Calcium	8.5 mg/dL	10.2 mg/dL	NLM			
Glucose						
Fasting	70 mg/dL	100 mg/dL	NLM			
Random		125 mg/dL	NLM			
Creatinine						
Male	0.7 mg/dL	1.3 mg/dL	NLM			
Female	0.6 mg/dL	1.1 mg/dL	NLM			
Total Protein	6.0 gm/dL	8.3 gm/dL	NLM			
Bicarbonate	23 mEq/L	29 mEq/L	NLM			
Procalcitonin	N/A	N/A	NLM			

CONFIDENTIAL Page 52 of 56

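### Table 6-2 grades white cell count on one row labelled as an increase, with a low-side limit only at Grade 4, so the graded shift tables cannot show moderate leukopenia and can show some falls as improvement

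*SAP*

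**What the plan says.** - SAP Section 6.2, Table 6-2: one row for white cells, "WBCs Increase". Grade 0 is 1,000 to 10,999/mm³, Grade 1 is 11,000 to 13,000, Grade 2 is 13,000 to 15,000 and Grade 3 is 15,000 to 30,000. Grade 4 is ">30,000 or <1,000". The stated source is the DMID scale.
- SAP Section 6.3, Table 6-5: the lower limit of normal for white cells is "4,500 cells/mcL" (the same unit as /mm³).
- SAP Section 6.1, Table 6-1: the worst white cell value is "Both highest value and lowest value".
- SAP Section 5.4.2: "The normalized laboratory values will be classified by toxicity grade according to the toxicity grading scales in SAP Section 6.2". "Shift tables will be presented to show the number of subjects with each toxicity grade at baseline versus each post-baseline visit", and for the worst post-baseline grade. Where high grades exist at both ends of a parameter, "shifts in toxicity will be presented for high and low toxicities separately". A further table counts subjects with "at least a 2-grade increase from baseline at any post-baseline study visit".
- SAP Section 3.12: the table of shifts of two or more grades is one of the five unblinded interim tables.

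**The concern.** A row that describes itself as grading increases also holds one low-side criterion, at the most severe grade, with nothing between it and Grade 0. Counts well below the SAP's own lower limit of normal are therefore classed with normal counts. High and low toxicity share one ordinal scale, so a change of grade does not say which way the count moved.

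Safety is a primary objective, and these grades feed the laboratory shift tables for Part A, Part B and both parts combined. Sodium, potassium, glucose and calcium each have separate low and high rows in Table 6-3; white cells do not. A programmer who follows Section 5.4.2 has to decide whether the separate-direction rule applies to white cells and, if it does, has no low-side grades other than 0 and 4.

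**Working it through.** **Inputs.** The white cell and neutrophil rows of Table 6-2, the normal limits of Table 6-5, and the shift and ≥2-grade rules of Section 5.4.2.

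**1. The ungraded low range.** Counts from 1,000 up to 4,500 are Grade 0 but below the lower limit of normal. That is (4,500 − 1,000)/4,500 = 78% of the range below the limit. The count must fall to 1,000/4,500 = 22% of the limit before any low grade is assigned. For comparison, hemoglobin leaves Grade 0 at 10.5 gm/dL against limits of 13.8 (male) and 12.1 (female), which is 76% and 87%, and then passes through Grades 1 to 4. No other row in Tables 6-2 to 6-4 grades a direction at Grade 4 alone.

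**2. Example shifts.** The single scale takes the row as printed. The split scale applies the separate-direction rule, with low side Grade 0 or 4 only.

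| Baseline → post-baseline | Single scale | Change | ≥2-grade flag | Split: high side | Split: low side |
|---|---|---|---|---|---|
| 8,000 → 1,000 | 0 → 0 | 0 | no | 0 → 0 | 0 → 0 |
| 8,000 → 999 | 0 → 4 | +4 | yes | 0 → 0 | 0 → 4, flagged |
| 12,000 → 1,500 | 1 → 0 | −1 | no | 1 → 0 | 0 → 0 |
| 20,000 → 1,500 | 3 → 0 | −3 | no | 3 → 0 | 0 → 0 |
| 20,000 → 999 | 3 → 4 | +1 | no | 3 → 0 | 0 → 4, flagged |

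The two readings disagree on the last line. On either reading the 1,000 to 4,499 range is invisible, and 20,000 → 1,500 appears only as improvement.

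**3. Overlapping bounds.** A rise from 8,000 to exactly 13,000 is Grade 0 to 1 (not flagged) or 0 to 2 (flagged). A rise from 12,000 to exactly 15,000 is Grade 1 to 2 (not flagged) or 1 to 3 (flagged).

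**4. What the neutrophil row recovers.** Neutrophil count = white cell count × neutrophil fraction. Table 6-5 gives a normal fraction of 40% to 60%, used here as an assumption.
- At 1,100 white cells: 1,100 × 0.40 = 440 (Grade 4) to 1,100 × 0.60 = 660 (Grade 3). At a baseline of 8,000 the neutrophils are 3,200 to 4,800 (Grade 0). This subject is flagged on the neutrophil row.
- Neutrophils reach Grade 2 (below 1,000) when white cells fall below 1,000/0.60 ≈ 1,670 to 1,000/0.40 = 2,500.
- From there up to 4,499, neither row gives a two-grade shift to a subject who starts at neutrophil Grade 0. With a higher neutrophil fraction the threshold falls further, towards 1,000/1.00 = 1,000.

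**5. Normalization.** Grades use normalized values, s = x × U_s/U_x, with U_s = 10,000. The raw count that normalizes to 1,000 is 1,000 × U_x/10,000. For an assumed local upper limit of 9,000 to 12,000 it is 900 to 1,200. The cut-off shifts between laboratories, but the gap remains.

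**The case against.** Much can be said for leaving the row alone, and several stronger readings fail.

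- **A contradiction with Table 6-1.** A reader might infer that taking both extremes as worst values promises two-sided grading. It does not: Section 5.4.2 uses that table for descriptive statistics. Neutrophils and platelets are also two-sided there and graded only for decrease, and lymphocytes, monocytes and chloride have no grading row.
- **Grade 0 must start at the lower limit of normal.** Other rows do not follow that rule either: hemoglobin is Grade 0 above 10.5, potassium above 3.4 against 3.7, and glucose above 64 against 70. What sets white cells apart is the size of the gap and the absence of any step between Grade 0 and Grade 4.
- **Leukopenia is lost altogether.** It is not. The lowest post-baseline white cell count is summarized with its change from baseline, listings mark values outside normal limits, and the neutrophil row would usually catch a deep fall.
- **The interim decision is compromised.** The documents do not show this. The criteria sit in a memo that is not available, and adverse event tables are also in the interim set.
- **The row comes from an external scale.** Whether it was copied faithfully cannot be checked here. The SAP takes albumin from CTCAE and bicarbonate from DAIDS, so it is not bound to one source.

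These points narrow the concern. They do not repair a row whose label and content disagree, whose bounds overlap, and which gives the separate-direction rule no graded low side.

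**Conclusion.** The point holds within limits. Followed as written, the white cell shift and ≥2-grade tables cannot show leukopenia between 1,000 and 4,499/mm³. They can present a fall from leukocytosis into leukopenia as improvement and, on the single scale, they miss a fall from 20,000 to 999. Exactly 13,000 and exactly 15,000 have no unique grade.

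The practical loss is mainly graded moderate leukopenia and falls in lymphocytes or monocytes, which have no grading row of their own. At a neutrophil fraction of 40% to 60%, the neutrophil row gives no two-grade shift above about 1,670 to 2,500 white cells. That range assumes the SAP's normal differential, which may not hold in ill subjects.

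The effect is confined to the graded tables, including one of the five interim tables. It does not touch the efficacy analyses, and nothing in the documents shows that it changed a decision. It should be corrected, because safety is a primary objective and the repair is small.

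**What to change.** Replace the white cell row in Table 6-2 with two rows:
- **Increase:** keep the high-side grades, remove the low-side limit from Grade 4, and write the bounds so that each value, including a non-integer normalized one, has exactly one grade.
- **Decrease:** graded low-side cut-offs that the sponsor selects and documents from a scale the SAP already cites. The SAP gives none for white cells below Grade 4, so no figures are proposed here. Grade 1 need not start exactly at 4,500, but the choice should be stated.

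State in Section 5.4.2 that white cell shifts and increases of two or more grades are tabulated separately by direction.

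The cost is one added table row and reprogramming of the affected shift tables, with no new data. Section 9 records a change in the normalization method, so any graded output made under an earlier SAP version has to be regenerated in any case.
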